1.0 Rationale and Specific Aims

While the barriers to community reintegration after traumatic brain injury (TBI) are multifactorial, memory and learning deficits are the most frequent targets for intervention in patients with TBI. The ability to (re)learn information is critical to a person's potential to benefit from therapy, to follow medical recommendations, to maintain positive social relationships, and to be successful at school or work. Yet, the last several decades have seen limited progress in developing restorative therapies for memory and learning deficits in this population.

In the cognitive neuroscience literature, evidence has accumulated that people with and without brain damage learn more when the context of learning is varied across time and space. Yet, rehabilitation typically occurs in a constrained context (i.e., the same therapy room at the same time of day). In memory rehabilitation, each opportunity to retrieve information strengthens that information in the neocortex, and is thus both an opportunity for assessment and intervention. Increasing the contextual variance of learning opportunities (i.e., in the daily lives and contexts of patients) may improve the rehabilitation potential of patients with TBI, in addition to increasing the potential for interventions that extend beyond an acute timeframe for service delivery.

There is critical need for technologies that move beyond the constrained therapy context to deliver interventions across time and space. In the proposed study, we focus on developing a technology-delivered system that extends the timing and context of memory exposures beyond current service delivery models. We aim to refine the technology for future use in research assessment and intervention contexts, with the long-term goal of improving memory care for individuals with TBI in their daily lives and across the lifespan. After taking into account feedback from real users, this system may also eventually be extended to other areas of TBI management and has the potential to improve both short-term and chronic care for the millions of Americans currently living with brain injury-related disability.

This is a pilot and feasibility study for a mobile phone-delivered intervention for memory, called MEMI (memory ecological momentary intervention), that was designed to support adults with chronic traumatic brain injury with their memory. The goal of the study is to examine the feasibility and acceptability of MEMI and to assess preliminary efficacy as to whether technology-delivered spaced memory retrieval opportunities improve memory in people with and without a history of chronic traumatic brain injury.

2.0 Inclusion/Exclusion Criteria

Inclusion criteria:

Pilot and Feasibility of MEMI for Chronic Traumatic Brain Injury

NCT06375421

For participants with TBI:

- Moderate-severe TBI. All participants sustained an injury of adequate effect to have been hospitalized. Severity is determined per the Mayo Classification System.
- All participants are at least 6 months post-injury at the time of study enrollment and thus exhibit chronic and stable neuropsychological profiles.
- All participants sustained their TBIs in adulthood (i.e., 18 years old or older) and are 60 years old or younger to limit the effects of age-related cognitive decline.

For all participants:

- Oral and written language skills sufficient for the study tasks.
- Participants must own a smartphone to access the Gorilla online behavioral experiment platform from their mobile phones.

Exclusion criteria:

For participants with TBI:

- History of medical or neurological disease affecting the brain or language, before or after the qualifying TBI.

For non-injured comparison peers:

- History of neurological or cognitive disability, including TBI

For all participants:

- Any disability (e.g., vision impairment, hard of hearing, aphasia or other neurologic condition) that limits ability to read, type, or verbally communicate.
- Demonstrates inability to receive and respond to a text message.

3.0 Enrollment/Randomization

No randomization will occur. The order of condition/word list combination will be pre-determined, and participants will be assigned to the next available combination based on when they join the study (i.e., a counterbalanced within-person crossover design).

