4.0 Study Procedures

The technology being tested involves receiving intermittent text messages over the course of a week with links to respond to memory prompts on the Gorilla mobile behavioral experiment webpage.

Pilot and Feasibility of MEMI for Chronic Traumatic Brain Injury
NCT06375421

This pilot will include 40 participants: 20 with a history of chronic moderate-severe TBI and 20 demographically-matched non-injured peers. Participation in the study will last two weeks for each person, with one week in each of two conditions:

- **Blocked (Active Comparator) Condition:** Participants complete their initial learning session on the target words, then immediately receive all of the exposures to each of the items in a single block. They do not complete any more retrieval sessions until one week later, when they complete a 15-minute test for their memory of all of the trained items.
- **MEMI Spaced Retrieval (Intervention) Condition:** Participants complete their initial learning session, and the subsequent retrieval sessions are spaced out over the course of the week (two short retrieval sessions each day) using MEMI. Then, they complete a 15-minute test for their memory of all of the trained items at the end of the week.

Outcome measures include:

- **Acceptability (Primary): Acceptability of Intervention Measure:** At the end of each week, participants complete this four-item measure regarding the acceptability of each intervention condition. Scores range from 4 to 20, with higher scores indicating higher acceptability.
- **Feasibility (Primary): Session Engagement:** In each condition, we measure the number of possible sessions that each participant completes. In the Blocked condition, the total number of possible sessions is two. In the MEMI condition, the number of possible sessions is 12. Higher number of sessions completed indicates better engagement and higher feasibility.
- **Efficacy (Secondary/Preliminary): Memory at 1 week:** At the end of each week, participants complete memory tasks to assess their memory for the trained information. Measures include:
 - *Free recall of word forms:* The number of target word forms that participants can free type without cueing (0=did not remember any words- worse to 16=remembered all the words - better)

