**NCT06375421 – Statistical analysis plan**

For this pilot study, we calculated descriptive statistics for participant characteristics, engagement (number of sessions completed), acceptability (Acceptability of Intervention Measure), and preliminary efficacy using R. Baseline participant characteristics were calculated for each group (TBI and non-injured comparison groups). Engagement, acceptability, and preliminary efficacy analyses were conducted within each group between the two conditions (Intervention: MEMI and Active Comparator: Blocked). For preliminary efficacy, we used paired-samples t-tests within each group to compare free recall at the 1-week assessment between the two conditions. We also conducted supplementary analyses assessing cued word form recall and cued definition recall at the 1-week assessment. Analyses were conducted using a complete-case approach.

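### The protocol does not say that condition order and word list are counterbalanced separately in the TBI and peer groups, although every condition comparison is made within a group

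*Protocol*

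**What the plan says.** Protocol section 3.0 is the whole allocation plan. It states "No randomization will occur", then "The order of condition/word list combination will be pre-determined", and then that "participants will be assigned to the next available combination based on when they join the study". It calls the result "a counterbalanced within-person crossover design". It does not give the number of combinations. It also does not say whether the two groups share a list or have one each, or at what level the counterbalancing is meant to hold.

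Protocol section 4.0 sets the sample at 40, "20 with a history of chronic moderate-severe TBI and 20 demographically-matched non-injured peers", with each person followed for two weeks, "with one week in each of two conditions". It says nothing about the order in which TBI participants and peers are enrolled.

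The SAP makes its comparisons inside the groups: "Engagement, acceptability, and preliminary efficacy analyses were conducted within each group between the two conditions". For efficacy, "we used paired-samples t-tests within each group to compare free recall at the 1-week assessment between the two conditions". It names no term for week, order or word list, and it uses complete cases only.

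**The concern.** With no randomization, counterbalancing is the design's only stated protection against two nuisance effects. One is a change from week 1 to week 2, for example practice with the learning and test format. The other is a difference in difficulty between word lists. Both cancel from a mean paired difference only if order and list pairing are balanced among the people averaged. Here those people are one group of 20, not all 40.

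A rule based on joining time balances whatever set of people the list runs over. If that set is all 40, each group may still be unbalanced, and an unadjusted paired t-test counts the leftover week or list effect as a MEMI effect. If every member of a group had the same list paired with MEMI, no later analysis of that group could separate list from condition. The same holds for week if every member had the same order.

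**Working it through.** The documents give no balance or power calculation, so there is no stated figure to reproduce. The check asks what the written rule guarantees within a group.

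**Inputs from the documents.** 40 people, 20 per group; two one-week periods; assignment by joining time; comparison within group; paired t-test without order or list terms.

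**Assumptions, not in the documents.** One list shared by both groups; each combination used equally often; two orders, or four combinations (two orders by two list pairings); the joining pattern; the size of the week effect; a two-sided 0.05 level for the error rates.

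**Bias formula.** Let τ be the MEMI effect and π the additive change from week 1 to week 2. The MEMI-minus-Blocked difference has mean τ + π for a person who has MEMI second and τ − π for a person who has MEMI first. The group mean is therefore τ + π × (n second − n first)/n.

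- 10:10 gives 0 × π.
- 12:8 gives (12 − 8)/20 = 0.20 × π in absolute size.
- 14:6 gives (14 − 6)/20 = 0.40 × π.
- 20:0 gives the whole of π.

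The same formula holds for list difficulty, with list pairing in place of order. As illustration only, a practice gain of 2 words would add 0.2 × 2 = 0.4 words at 12:8, on the 0 to 16 scale.

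**Arbitrary joining order, two orders.** The number k of MEMI-first people in a group is hypergeometric: P(k) = C(20,k) × C(20,20−k) / C(40,20).

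- P(10:10) = 184,756² / 137,846,528,820 = 0.248.
- P(11:9 either way) = 2 × 167,960² / 137,846,528,820 = 0.409.
- P(12:8 or worse) = 1 − 0.248 − 0.409 = 0.343.
- P(13:7 or worse) = 0.113, and P(14:6 or worse) = 0.026.
- The mean absolute imbalance is 12% of the group, so on average about 0.12 × π enters the estimate.

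**Arbitrary joining order, four combinations.** Order and list pairing are both exactly 10:10 with probability Σ C(10,a)⁴ / C(40,20) = 0.061, summing a from 0 to 10. At least one of them is 12:8 or worse with probability 0.57.

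**Regular joining patterns.** Let A = MEMI first with list 1 in MEMI, B = MEMI first with list 2 in MEMI, C = Blocked first with list 1 in MEMI, D = Blocked first with list 2 in MEMI.

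| Pattern | TBI group receives | Peers receive | Result |
|---|---|---|---|
| One whole group first, then the other | 5 of each | 5 of each | Balanced |
| Strict alternation, cycle A-B-C-D | A, C | B, D | Order 10:10; list fully confounded, opposite sign in the two groups |
| Strict alternation, cycle A-C-B-D | A, B | C, D | List 10:10; order fully confounded |
| Strict alternation, cycle A-B-D-C | A, D | B, C | Additive week and list effects both cancel |

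**Effect on the paired t-test.** Simulated type I error (n = 20, 100,000 runs), with the week effect in SDs of the paired difference:

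| Week effect | 10:10 | 12:8 | 14:6 | 20:0 |
|---|---|---|---|---|
| 0.5 SD | 0.030 | 0.044 | 0.096 | 0.564 |
| 1 SD | 0.006 | 0.029 | 0.165 | 0.989 |

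The rates below 0.05 arise because an unmodelled week effect also inflates the SD of the differences. The estimate at 12:8 is still shifted by 0.20 × π.

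**After the change.** With one list per group, 20 divides exactly into 10:10 or 5:5:5:5, and additive week and list effects cancel before any complete-case losses.

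**The case against.** A reader might infer that a single running sequence covers both groups. The protocol does not say so. It is silent on one list or two, and a separate list for each group fits the wording equally well. That objection stands, so the point is limited to what is not assured.

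A reader might also infer from the alternation example that list and condition are in fact confounded here. That too is unsupported. It needs a shared list, four combinations, a particular cycle and strict alternation, none of which is stated, and one of the three cycles shown does no harm even then. Demographic matching makes interleaved enrolment plausible but does not imply it; peers could equally have been recruited after the TBI participants, which is harmless.

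The typical consequence is also small. Under arbitrary joining, 12:8 or better has probability 1 − 0.113 = 0.887, and the simulated error rate at 12:8 stays below 0.05. Acceptability and engagement are the primary outcomes. List difficulty and practice are arguments about recall, and no effect on the primary outcomes has been quantified. The protocol calls this phase descriptive.

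What remains is that within-group balance is not secured in writing and the named test would not correct for its absence. Preliminary efficacy is a stated aim, and the results are meant to inform later trials.

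**Conclusion.** The point holds as a gap in specification. Assignment is by joining time with no stated separation by group, the comparisons are within group, and the recall test is unadjusted. Balance of week and list effects in each group of 20 is therefore not assured. The documents do not show that imbalance occurred.

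Under a shared list and arbitrary joining (both assumed), the usual cost is about 12% to 20% of whatever week effect exists. Complete confounding is possible only under regular interleaving with an unfavourable cycle. With separate lists, or with one group enrolled first, the problem is absent apart from balance lost through complete-case exclusions. Importance is modest, because the exposed outcome is secondary and preliminary in a descriptive pilot.

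**What to change.** **If enrolment is still open.** State in section 3.0 that TBI participants and peers are assigned from separate counterbalancing lists, each cycling through all combinations. This costs one sentence and a second list, with no extra participants or visits.

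**If enrolment is complete**, as the SAP's past tense suggests:

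- State whether one list or two was used.
- Tabulate order by list pairing within each group, among complete cases.
- Where a group is unbalanced, base its recall comparison on the unweighted mean of the combination-specific differences. Alternatively, take the intercept from regressing the paired difference on order and list pairing. Code each as +1 and −1; codes centred at the group's own mean would simply return the raw mean. Use the regression if one of four combinations is empty.
- If a group has only one list pairing, state that list cannot be separated from condition in that group. If it has only one order, state the same for week.

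The cost is a small table, slightly more analysis work and a few degrees of freedom: 17 instead of 19 with 20 complete cases and two added terms. The loss of precision is slight. Adjusting for a 12:8 order split multiplies the variance by (1/12 + 1/8)/4 ÷ (1/20) = 1.04 at the same residual SD, and removing a real week effect lowers that SD.

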4.0 Study Procedures

The technology being tested involves receiving intermittent text messages over the course of a week with links to respond to memory prompts on the Gorilla mobile behavioral experiment webpage.

Pilot and Feasibility of MEMI for Chronic Traumatic Brain Injury
NCT06375421

This pilot will include 40 participants: 20 with a history of chronic moderate-severe TBI and 20 demographically-matched non-injured peers. Participation in the study will last two weeks for each person, with one week in each of two conditions:

- **Blocked (Active Comparator) Condition:** Participants complete their initial learning session on the target words, then immediately receive all of the exposures to each of the items in a single block. They do not complete any more retrieval sessions until one week later, when they complete a 15-minute test for their memory of all of the trained items.
- **MEMI Spaced Retrieval (Intervention) Condition:** Participants complete their initial learning session, and the subsequent retrieval sessions are spaced out over the course of the week (two short retrieval sessions each day) using MEMI. Then, they complete a 15-minute test for their memory of all of the trained items at the end of the week.

Outcome measures include:

- **Acceptability (Primary): Acceptability of Intervention Measure:** At the end of each week, participants complete this four-item measure regarding the acceptability of each intervention condition. Scores range from 4 to 20, with higher scores indicating higher acceptability.
- **Feasibility (Primary): Session Engagement:** In each condition, we measure the number of possible sessions that each participant completes. In the Blocked condition, the total number of possible sessions is two. In the MEMI condition, the number of possible sessions is 12. Higher number of sessions completed indicates better engagement and higher feasibility.
- **Efficacy (Secondary/Preliminary): Memory at 1 week:** At the end of each week, participants complete memory tasks to assess their memory for the trained information. Measures include:
 - *Free recall of word forms:* The number of target word forms that participants can free type without cueing (0=did not remember any words- worse to 16=remembered all the words - better)
 - *Cued recall of word forms:* The number of target word forms that participants remember in response to prompting (i.e., typing the word that labels a given image) (0=did not remember any words- worse to 16=remembered all the words - better)
 - *Cued recall of word meanings:* The number of target word meanings that participants remember in response to prompting (i.e., typing the definition for a given word) (0=did not remember any words- worse to 16=remembered all the words - better)
- **Other: Number of Spatial Contexts:** At the beginning of each retrieval session, we ask participants to give their spatial context (the physical location in which they are completing the session, e.g., home or work). We report the number of different spatial contexts in which participants

completed sessions in each condition. A higher number of spatial contexts indicates more variance in the contexts of retrieval opportunities, which is a goal of this technology.

5.0 Reporting of Adverse Events or Unanticipated Problems involving Risk to Participants or Others

Although serious adverse events are unanticipated given the nature of this study, the PI will evaluate all participant concerns for severity, relationship to the research, and actions to be taken, and immediately report any serious adverse events or unanticipated problems involving risks to participants to the IRB.

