7.0 Statistical Considerations

This phase of the study is descriptive and is designed to inform the research team regarding which aspects of using MEMI are challenging, or represents a barrier to use, for individuals with TBI. We collect preliminary pilot data on acceptability, feasibility, and the effects of technology-delivered spaced retrieval on memory in TBI. These findings will be used to refine the technology for future research and clinical trials.

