8.0 Privacy/Confidentiality Issues

Only KSP approved by the IRB will have access to research information. Participant survey data will be entered and stored electronically in REDCap. KSP will assign participants a unique subject ID associated with their identifiable information in REDCap. Original paper copies of any surveys will be de-identified and filed in a locked file cabinet. Participant contact information will be password protected and stored separately from research data, without any health information, on a secure VUMC server. Participant information collected for payment purposes will be stored separate from research data in a locked file cabinet.

In order to minimize the risks of loss of privacy, all research-related conversations with participants will take place in private testing rooms on a private web conference session or phone call when data are collected remotely. Recordings from participant interviews will be saved with the unique subject ID

Pilot and Feasibility of MEMI for Chronic Traumatic Brain Injury

NCT06375421

on a secure VUMC server. Twilio, the platform that delivers the mobile phone intervention, is integrated into REDCap in order to initiate and tailor the intervention (e.g., name, cell phone number, preferred time of day to receive text messages). Twilio will be used to send text messages at pre-designated times. Each of these messages contains a link to the secure web platform where participants will complete the memory task. Individual participant responses to the memory task are only accessible by KSP through a secure password protected portal.

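### Does the shorter gap between last practice and test in the MEMI week undermine the 1-week recall comparison?

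*Protocol*

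**What the plan says.** Protocol section 4.0 describes two one-week conditions, both taken by every participant. In Blocked, participants learn the words and "then immediately receive all of the exposures to each of the items in a single block". After that, "They do not complete any more retrieval sessions until one week later, when they complete a 15-minute test". In MEMI, "the subsequent retrieval sessions are spaced out over the course of the week (two short retrieval sessions each day) using MEMI", and the test comes at the end of that week.

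The Session Engagement outcome gives the counts: "In the Blocked condition, the total number of possible sessions is two", and "In the MEMI condition, the number of possible sessions is 12". The text does not say whether the 12 include the learning and test sessions, and it does not give the interval from the last MEMI session to the test.

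Protocol section 3.0 counterbalances condition order and word list. The SAP uses paired t-tests within each group to "compare free recall at the 1-week assessment between the two conditions". Section 4.0 labels recall secondary and preliminary; the primary outcomes are acceptability and session engagement. Section 7.0 calls this phase descriptive and says it collects pilot data on, among other things, "the effects of technology-delivered spaced retrieval on memory in TBI".

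**The concern.** A memory test depends on how practice was distributed and also on how long ago it ended. Here both change with condition. Blocked participants are tested a week after they last saw the items, and MEMI participants within a few days at most. Under ordinary forgetting MEMI would score higher even if spacing had no benefit.

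Counterbalancing does not help, because it balances order and word list, whereas the lag travels with the condition. The paired difference carries the lag difference in full for each participant. A covariate for lag would not help either, since condition almost fully determines it.

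At stake is attribution. If a MEMI advantage were credited to spacing itself, a later trial could be built on an effect that is partly recent practice. The aims in protocol section 1.0 and the wording of section 7.0 both mention spaced retrieval, so that reading is available.

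**Working it through.** The documents give no lag, forgetting rate, standard deviation, alpha or power, so there is no figure of the plan to reproduce. The check has three steps.

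**1. Bound the MEMI lag.** Inputs from protocol section 4.0: 12 possible sessions and two retrieval sessions a day. Take learning as day 0 and the test as day 7. Lag = 7 − day of last retrieval session.

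| Retrieval sessions among the 12 | Days needed | First day | Last day | Lag (days) |
|---|---|---|---|---|
| 12 (or 11) | 6 | 0 | 5 | 2 |
| 12 (or 11) | 6 | 1 | 6 | 1 |
| 12 (or 11) | 6 | 2 | 7 | 0 |
| 10 (learning and test counted) | 5 | 0 | 4 | 3 |
| 10 | 5 | 1 | 5 | 2 |
| 10 | 5 | 2 | 6 | 1 |

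Blocked's two sessions look like one learning-plus-exposure sitting and one test. Counting MEMI the same way leaves 10 retrieval sessions; starting the day after learning they end on day 5, a lag of 2 days. A lag of 1 day fits better if all 12 are retrieval sessions. The text does not decide between them. Over all layouts the lag is 0 to 3 days against 7, so the conditions differ by 7 − 3 = 4 to 7 − 0 = 7 days.

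**2. See what recency alone could do.** Assume no spacing benefit, MEMI recall of 8 of 16 words, recall falling as time to the power −b with b from 0.1 to 0.3, and a Blocked lag of 7 days.

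- Only the last exposure counts: gain = 8 − 8 × (7/lag)^−b. Lag 1 gives 1.41 to 3.54 words, lag 2 gives 0.94 to 2.51, lag 3 gives 0.65 to 1.80.
- Each day's exposures decay separately with equal weight: gain = 8 − 8 × 7^−b / mean(lag^−b). Practice at lags of 1–5 days gives 0.76 to 2.14 words; at lags of 3–7 days, 0.30 to 0.89.
- A curve that also allows lag 0, recall = 16 × A × (1 + t)^−b with A from 0.5 to 0.8: lag 1 gives 0.97 to 3.54 words and lag 3 gives 0.47 to 1.59. At lag 0 the gain is 16 × A × (1 − 8^−b), from 8 × (1 − 0.812) = 1.5 to 12.8 × (1 − 0.536) = 5.9.

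Turning words into a chance of significance is less stable still. With n = 20 and two-sided alpha 0.05 (assumed), a gain of 2.58 words (b = 0.2, lag 1, last exposure only) is significant with probability 0.95 if the SD of differences is 3, and 0.78 if it is 4. If MEMI recall is 4 of 16 the gain halves to 1.29 words and the probability at SD 3 is 0.45. The smallest case, 0.30 words, gives 0.07. The documents support the direction but no particular size.

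**3. Ask whether the design could avoid it.** Equalising the lag at 7 days would move the MEMI test from day 7 to between day 4 + 7 = 11 and day 7 + 7 = 14. Learning-to-test would then be 11 to 14 days in MEMI against 7 in Blocked. With both conditions starting on day 0, one interval can be matched only by unmatching the other.

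**The case for a change.** The strongest case for acting is that the question in section 1.0 is whether spaced retrieval improves memory, the SAP runs inferential tests under the heading of efficacy, and section 7.0 says the results will inform future trials. The bias, if spacing is taken as the target, runs in the intervention's favour and is at least 4 days of lag on any reading. A statement of the lag and a limit on the conclusion would cost only a few sentences.

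Part of this stands. The lag difference is real, and a MEMI advantage would not by itself show that spacing was the cause. What does not stand is that the plan gives a wrong answer to its own question. Section 4.0 names the intervention arm as MEMI spaced retrieval, so the wording in section 7.0 can be read as the name of the package. That section reports no result, and the SAP compares two conditions without naming a mechanism. The added sentences would alter no estimate, test, outcome or design feature.

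Much of what a careful reader would want is already there. Sessions completed by condition are a primary outcome, which covers a good part of the exposure received. Section 8.0 says "Twilio will be used to send text messages at pre-designated times", so the scheduled lag should be known to the team when it writes up. Missed MEMI sessions work the other way, lowering exposure and possibly lengthening the lag; that belongs to the programme as delivered.

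**Conclusion.** The unequal lag is a fair trade-off, and the plan needs no change. Both conditions are tested at the same time from learning, which is a legitimate pragmatic contrast, and the paired t-test estimates it properly: one week of MEMI as delivered against a single block, both about a week after learning. Being practised closer to the test is part of what the MEMI week consists of.

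The limit is one of interpretation. Time since last exposure is about 7 days in Blocked and 0 to 3 days in MEMI (inferred from session counts, with learning on day 0 and test on day 7), so the comparison cannot divide a MEMI advantage between spacing and recency. Recency favours MEMI. Its size ranges from about 0.3 to 3.5 words of 16 at lags of 1 to 3 days, and could be larger if the last session falls on the test day, all on assumed forgetting rates and recall levels. Those assumptions are too loose to support any stated false-positive rate. Acceptability and session engagement, the primary outcomes, are unaffected. An analyst reporting this descriptive pilot can be expected to describe the recall result as a package effect.

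### Session Engagement, a primary outcome, is a raw count out of 2 (Blocked) or 12 (MEMI), so comparing the conditions mainly shows how many sessions were offered

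*Protocol*

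**What the plan says.** Protocol section 4.0 lists Session Engagement as the primary feasibility outcome: "In each condition, we measure the number of possible sessions that each participant completes". The maxima follow: "In the Blocked condition, the total number of possible sessions is two. In the MEMI condition, the number of possible sessions is 12". The rule for reading the outcome is "Higher number of sessions completed indicates better engagement and higher feasibility".

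The SAP keeps the same scale, "engagement (number of sessions completed", and summarises it descriptively. It also says that engagement, like acceptability and preliminary efficacy, was analysed within each group by comparing MEMI with Blocked. The paired t-test is named only for free recall. Neither document gives a percentage or any other scaling to the number of sessions offered, and neither names a test, a subtraction or a threshold for engagement.

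The sample is "20 with a history of chronic moderate-severe TBI and 20 demographically-matched non-injured peers", and each person goes through both conditions.

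**The concern.** The SAP puts three kinds of outcome side by side between conditions. Acceptability runs from 4 to 20 in both conditions, and each recall measure runs from 0 to 16 in both. Engagement alone has a different ceiling in each condition.

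A count is adherence multiplied by sessions offered. When six times as many sessions are offered in one condition, the counts differ widely even if participants are equally diligent in both. Combined with a rule that a higher number means higher feasibility, the comparison favours MEMI almost regardless of behaviour. A group could complete everything asked of it under Blocked and only half of what MEMI asked, and the table would still show the larger figure for MEMI. In a descriptive pilot the reported figures are the result, so the scale of a primary outcome matters even though nothing is tested.

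**Working it through.** **Inputs.** The maxima of 2 (Blocked) and 12 (MEMI) and the group size of 20 come from Protocol section 4.0. The documents give no adherence figures, so all adherence values below are assumptions shown over a range. There is no sample-size or power derivation for this outcome to reproduce; the only stated figures are the two maxima.

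**Formulae.** Let pB and pM be the proportions of possible sessions completed under Blocked and MEMI.

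- Mean counts: Blocked = 2 × pB, MEMI = 12 × pM.
- At equal adherence p: ratio = 12p / 2p = 6, difference = 12p − 2p = 10p.
- The MEMI count is higher when 12 × pM > 2 × pB, that is, when pM > pB/6.
- Count and percentage point in opposite directions when pB/6 < pM < pB.

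**Equal adherence.** The percentage difference is 0 in every row.

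| Adherence in both | Blocked count | MEMI count | Count difference |
|---|---|---|---|
| 100% | 2.0 | 12.0 | +10 |
| 80% | 1.6 | 9.6 | +8 |
| 50% | 1.0 | 6.0 | +5 |

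**MEMI adherence above which its mean count is the higher one (pB/6).**

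| Blocked adherence | MEMI adherence |
|---|---|
| 100% | 16.7% |
| 90% | 15.0% |
| 75% | 12.5% |
| 50% | 8.3% |

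For a single participant with 2 of 2 under Blocked, the smallest MEMI count that exceeds 2 is 3, and 3/12 = 25%.

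**Reversals.**

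| Blocked | MEMI | Count difference | Percentage difference |
|---|---|---|---|
| 2/2 (100%) | 3/12 (25%) | 3 − 2 = +1 | 25 − 100 = −75 points |
| 2/2 (100%) | 6/12 (50%) | 6 − 2 = +4 | 50 − 100 = −50 points |
| 95% (mean 1.9) | 80% (mean 9.6) | 9.6 − 1.9 = +7.7 | 80 − 95 = −15 points |

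**Coarseness of the percentage.** One missed session costs 100/2 = 50 points under Blocked and 100/12 = 8.3 points under MEMI. In a mean over 20 participants, that is 50/20 = 2.5 points and 8.33/20 = 0.42 points.

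**What the maxima contain.** MEMI has "two short retrieval sessions each day", but the number of days is not given. Six days of retrieval alone gives 2 × 6 = 12. Five days plus the learning session and the test gives 2 × 5 + 1 + 1 = 12. Seven full days would give 14 for retrieval alone and 16 with learning and test. For Blocked, participants learn the words and "then immediately receive all of the exposures to each of the items in a single block"; learning and block in one sitting, followed by the test, would make 2, but that is inference. The documents do not say which sessions are counted, so 12 is compatible with them without being uniquely reproducible.

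**The case against.** The strongest reply is that the denominators belong to the outcome definition. The protocol counts completed sessions out of those possible, in each condition, and prints both maxima in the same bullet; anyone can divide. The higher-is-better sentence resembles the direction notes attached to the other measures and may only say which end of the scale is good. The stated purpose is "This phase of the study is descriptive and is designed to inform the research team regarding which aspects of using MEMI are challenging", and MEMI's own count out of 12 serves that purpose. No decision rests on the contrast, and every size above depends on an assumed adherence and a subtraction the documents do not specify.

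The percentage has weaknesses too. Under Blocked it can only be 0, 50 or 100%. If the SAP's complete-case approach also covers engagement and requires the 1-week test (neither is stated), and if the two Blocked sessions are as inferred above, retained participants would be at or near 2 of 2 almost by construction, and MEMI would be compared with a fixed 100%. A more modest remedy would report each condition against its own maximum and say that the two are not directly comparable.

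Much of this stands. The count is sound within a condition, the information about MEMI is not lost, and no test is biased. It does not remove the point, because the SAP itself sets engagement between conditions and keeps the raw number for doing so, and the only reading rule offered misleads for that comparison. A primary outcome should not need rescaling by the reader before its stated comparison makes sense. The weaknesses of the percentage are reasons to print the counts and denominators beside it.

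**Conclusion.** The concern holds and should be fixed. As written, the between-condition description of a primary outcome mainly reflects the number of sessions offered: a factor of six at equal adherence, and a reversed direction whenever MEMI adherence lies between one sixth of Blocked adherence and Blocked adherence itself.

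The factor of six follows from the stated maxima alone. The session differences and reversal examples rest on assumed adherence, and whether a reversal occurs in this trial cannot be known from the documents. The fault is limited to the scale of a descriptive comparison. Which sessions make up the 2 and the 12 is a separate clarification and adds nothing to the severity.

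**What to change.** In Protocol section 4.0 and the SAP:

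1. Report engagement for each participant and condition as the percentage of possible sessions completed, with the raw count and denominator beside it (x of 12, y of 2).
2. Base any between-condition description on the percentage.
3. Restrict the higher-is-better sentence to comparisons within a condition, or reword it to refer to a higher percentage of possible sessions.
4. State that the percentage was added after the outcome was first defined, and keep reporting the raw count. The SAP is written in the past tense, so a change to a primary outcome's scale needs this disclosure.

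As a clarification, list which sessions make up the 2 and the 12, on the same basis in both conditions, and say whether the complete-case rule applies to engagement.

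**Cost.** No new data are needed, since the percentage follows from the counts and the stated maxima. The contrast may look less favourable to MEMI. The Blocked percentage is coarse, and 2 and 12 sessions remain unequal burdens even as percentages, which the report should say.
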